5.2.4 Management of Infusion Reactions

Infusion-related reactions may occur during the infusion of study treatment. The infusion is to be administered at a site properly equipped and staffed to manage anaphylaxis should it occur. The patient should be observed for at least 60 minutes following the first infusion of study treatment. During this observation period, the IV line should remain open for at least 1 hour to allow administration of IV drugs if necessary. All supportive measures consistent with optimal patient care will be given throughout the study according to institutional standards. This includes adjusting the infusion time if necessary. Medications for infusion-related reactions, such as epinephrine, antihistamines, and corticosteroids, should be available for immediate use.

Patients who experience a Grade 1 or Grade 2 infusion-related reaction may receive subsequent study treatment infusions with premedication consisting of acetaminophen (650 mg orally) and diphenhydramine (25–50 mg orally or 10–25 mg IV) or according to institutional standards, administered 30–60 minutes prior to each 30-minute infusion. Additionally, steroids may be administered at the physician discretion.

5.2.5 Dose Modifications

Intra-patient dose reduction to 1.2 mg/kg will be allowed depending on the type and severity of toxicity. Table 3 on the following page describes the recommended dose modifications for study treatment-associated toxicity. The start of the next cycle may be delayed for up to 3 weeks if additional time is required for the patient to recover from study treatment-associated toxicity experienced during the current cycle. Delays of greater than 3 weeks are generally prohibited; if a delay of greater than 3 weeks is anticipated, the QAM and the PI should be contacted for consideration. Approval of such delays will be on a case-by-case basis.

NOTE: SGN-35 doses reduced for treatment-related toxicity should not be re-escalated.

NOTE: Please use CTCAE version 4.0 for all treatment-associated toxicities.

NOTE: Additional dose reductions (in addition to Table 3) may be warranted on a case-by-case basis at the discretion of the PI. If the treating physician feels this is necessary, due to recurrent toxicity or other reasons, the treating physician must contact the PI and the QAM to discuss.

5.2.5.1 Dose modifications regarding pancreatitis.

- Asymptomatic elevated amylase and lipase (for patients with amylase elevation $>3\times$ upper limit of normal, but no abdominal pain):
 - Grade 1 – continue at same dose level
 - Grade 2 – continue at same dose level
 - Grade 3 – hold dose until toxicity resolves to \leq Grade 2 and then resume treatment at the same dose level
 - Grade 4 – hold dose until toxicity resolves to \leq Grade 2 and then resume treatment at reduced dose level or discontinue at the discretion of the treating investigator

If a 2nd episode of asymptomatic hyperamylasemia occurs, SGN-35 must be reduced by 1 dose level. If a 3rd episode occurs, SGN-35 must be permanently discontinued.

- Mild to moderate pancreatitis (hyperamylasemia syndrome – characterized by abdominal pain of <72 hours duration with amylase and/or lipase elevation): Hold SGN-35. May consider resuming, with 1 dose level reduction, when signs, symptoms and laboratory values (i.e., amylase and lipase) return to baseline/normalize. If a 2nd episode of mild to moderate pancreatitis occurs, SGN-35 must be permanently discontinued.

- Severe pancreatitis (abdominal pain of > 72 hours with lipase and/or amylase elevation of >3x normal for >72 hours duration): Permanently stop SGN-35.

Table 3. Recommended SGN35 Dose Modifications for SGN35 Treatment-Associated Toxicity.

• Toxicity	• Grade 1	• Grade 2	• Grade 3	• Grade 4
• Non-Hematologic^c (pancreatic^c)	
 Withhold dose until toxicity is returned to baseline, then resume treatment at the same dose level 	
 Withhold dose until toxicity is returned to baseline, then resume treatment at the same dose level 	
 Withhold dose until toxicity has returned to baseline, then reduce dose, as described in section 5.2.5.1. 	
 Withhold dose until toxicity has returned to baseline, then reduce dose, as described in section 5.2.5.1.
• Non-Hematologic; Other	
 Continue at same dose level. 	
 Continue at same dose level, except in the event of Grade 2 neuropathy. For Grade 2 neuropathy, withhold dose until toxicity is \leq Grade 1 or has returned to baseline, then resume treatment at the same dose level. For the second occurrence of Grade 2 neuropathy, withhold dose until toxicity is \leq Grade 1, then reduce the dose to 1.2 mg/kg (or to 0.8 mg/kg if already on 1.2 mg/kg) and resume treatment 	
 Withhold dose until toxicity is \leq Grade 1 or has returned to baseline, then resume treatment at the same dose level^a For Grade 3 or higher neuropathy, discontinue treatment. 	
 Withhold dose until toxicity is \leq Grade 1 or has returned to baseline, then reduce dose to 1.2 mg/kg (or to 0.8 mg/kg if already on 1.2 mg/kg) and resume treatment^a For Grade 3 or higher neuropathy, discontinue treatment.
• Hematologic	
 Continue at same dose level. 	
 Continue at same dose level. 	
 Withhold dose until toxicity is \leq Grade 2, or has returned to baseline, then resume treatment at the same dose level.^b Consider growth factor support (eg, G-CSF) for treatment of neutropenia and prophylaxis in subsequent cycles. 	
 Withhold dose until toxicity is \leq Grade 2, then resume treatment at the same dose level. Consider growth factor support (eg, G-CSF) for treatment of neutropenia and prophylaxis in subsequent cycles. For the second occurrence of Grade 4 toxicity (if neutropenia, while receiving growth factor support), withhold dose until toxicity is \leq Grade 2, then reduce the dose to 1.2 mg/kg (or to 0.8 mg/kg if already on 1.2 mg/kg) and resume treatment^b

^a Patients who develop Grade 3 or 4 electrolyte laboratory abnormalities or nausea/vomiting that respond to treatment may continue study treatment without interruption.

^b Patients who develop Grade 3 or 4 lymphopenia may continue study treatment without interruption.

^c See Section 5.2.5.1 above regarding specific modifications for pancreatitis.

5.2.6 Treatment Compliance.

Subject compliance with treatment is anticipated to be well controlled for this trial as study treatment will be administered at the study site by the investigator or investigator designee. Treatment administration data will be captured and reviewed to ensure site compliance with the treatment regimen.

5.2.7 Other directions.

See **Section 8.1** for Preparation, Packaging and Labeling, and Concomitant Therapy and other information regarding SGN35.

5.2.8 Re-staging.

The first 22 evaluable patients entered onto the trial will have an “early” FDG-PET scan performed after the 2 ‘lead in’ cycles of SGN35. The recommended timing for this FDG-PET scan is to be completed between days 14 and 18 after the 2nd cycle of SGN35. See **Section 6.6** for further details regarding completion and interpretation of FDG-PET and see Table 3 Schedule of Activities in Section 7.0 for additional details.

5.2.8.1 Re-staging for evaluable patients 23 through 45.

Patients 23 through 45 are not required to have a restaging PET or CT scan after the first 2 ‘lead in’ cycles of SGN35. PET and/or CT scans may be obtained at the investigators discretion at this time point. If there is documented progressive disease after SGN35 (i.e., prior to initiation of AVD), patients may still remain ‘on trial’ and proceed to AVD chemotherapy, however they will not receive SGN35 consolidation.

5.2.8.2 Re-staging for chemotherapy intolerant patients.

See Section 5.3.3.8 for this definition. Chemotherapy intolerant patients may proceed with consolidation SGN35 therapy if they have achieved either a PR or CR at time of chemotherapy intolerant designation. These patients should have repeat staging CT scans performed prior to initiation of SGN35 consolidation therapy (if not done within the preceding 30 days).

5.3 AVD chemotherapy.

5.3.1 Dosing.

Chemotherapy	Dose	Infusion	Timing
Doxorubicin (adriamycin)	25 mg/m ²	IV	Days 1 and 15
Vinblastine (velban)	6 mg/m ²	IV	Days 1 and 15
Dacarbazine	375 mg/m ²	IV	Days 1 and 15

(DTIC)			
--------	--	--	--

NOTE: A cycle is 28 days. Use actual weight to calculate body surface area. For further information regarding drug administration, please see Section 8.2.

5.3.2 Number of cycles.

Patients will receive 6 cycles of AVD chemotherapy, unless judged by the treating physician to be chemotherapy intolerant (see section 5.3.3.8). Each cycle is scheduled to be repeated every 28 days.

5.3.3 Dose modifications.

NOTE: All toxicities should be graded according to the CTC (version 4.0).

5.3.3.1 Hematologic Toxicity.

Dose delays and reductions of AVD chemotherapy only are to be done at the discretion of the treating physician and must be clearly documented on the Treatment eCRF in NOTIS along with the CTC (version 4.0) grade. Delays of greater than 3 weeks due to AVD toxicity must be approved by the PI and the QAM must be included on this correspondence. The following are only recommendations (are not mandatory) for modifications for AVD; SGN modifications are mandatory and are described above in Table 3. Some guidelines to be considered are for absolute neutrophil count of <500 on the day of treatment would be to consider addition of G-CSF (filgrastim) therapy. This is strongly preferred due to the long half-life of pegfilgrastim.

Patients with persistent severe neutropenia, especially despite use of granulocyte growth factor, could have reduction of doxorubicin and vinblastine by 25%.

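### The pain-free pancreatic enzyme rule in 5.2.5.1 counts amylase but not lipase, and it disagrees with the Table 3 pancreatic row with no statement of which governs

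*Combined protocol and SAP*

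**What the plan says.** Section 5.2.5.1 has three bullets. The first, for rises without symptoms, opens "Asymptomatic elevated amylase and lipase (for patients with amylase elevation" and goes on to require a value above 3 times ULN and no abdominal pain. It then sets actions by CTCAE grade. Grades 1 and 2 carry on unchanged. At Grade 3 the dose is held until the toxicity is no worse than "Grade 2 and then resume treatment at the same dose level". At Grade 4 it is held until no worse than "Grade 2 and then resume treatment at reduced dose level or discontinue at the discretion of the treating investigator". Repeats have their own rule: "If a 2nd episode of asymptomatic hyperamylasemia occurs, SGN-35 must be reduced by 1 dose level", and then "If a 3rd episode occurs, SGN-35 must be permanently discontinued". The other two bullets cover mild-to-moderate and severe pancreatitis. Both require abdominal pain, and both accept a rise in either enzyme.

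Table 3 has its own pancreatic row. At Grades 1 and 2 it holds the dose until baseline is regained and restarts at the same level. At Grades 3 and 4 it reads "Withhold dose until toxicity has returned to baseline, then reduce dose, as described in section 5.2.5.1". Footnote c refers the reader to 5.2.5.1 but does not rank the two texts.

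The status of Table 3 varies. Section 5.2.5 says "Table 3 on the following page describes the recommended dose modifications for study treatment-associated toxicity", and the table is titled "Recommended SGN35 Dose Modifications for SGN35 Treatment-Associated Toxicity". Section 5.3.3.1, in contrasting SGN-35 with AVD, treats the SGN-35 modifications in Table 3 as mandatory.

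Table 4 footnote 17 requires both enzymes to be drawn before SGN-35 dosing and sends the site to 5.2.5.1 for the action.

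**The concern.** There are two linked problems.

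First, a site holding a pain-free lipase result with normal amylase is sent to a rule whose heading includes lipase but whose entry condition and episode count do not. The symptomatic bullets name both enzymes as alternatives, so the narrower wording of the pain-free bullet reads as a real restriction or as an oversight. The text does not say which.

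Second, for a pain-free rise that does qualify, 5.2.5.1 and Table 3 give different recovery levels and, at Grade 3, different restart doses. Two sites reading the same protocol could give different next doses for the same laboratory result. Sections 5.2.5 and 5.4.3 advise against re-escalating a dose reduced for toxicity, so the choice would persist.

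The setting is a known risk. Section 1.6.5 calls acute pancreatitis an important potential risk of the drug and says it contributed to a fatal outcome in 2 patient reports.

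**Working it through.** No figure in the plan needs reproducing. The check is a comparison of the two texts, followed by a count of the doses affected.

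**Step 1. Which enzyme triggers what in 5.2.5.1**

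| Rule | Enzyme named |
|---|---|
| Pain-free bullet, heading | amylase and lipase |
| Pain-free bullet, entry condition (>3x ULN, no pain) | amylase only |
| Pain-free bullet, 2nd-episode reduction and 3rd-episode stop | amylase only (hyperamylasemia) |
| Mild-to-moderate pancreatitis | either |
| Severe pancreatitis | either |

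A pain-free rise in lipase alone does not meet the entry condition and does not count as an episode.

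**Step 2. Pain-free rise: 5.2.5.1 against the Table 3 pancreatic row**

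| Grade | 5.2.5.1 | Table 3 | Difference |
|---|---|---|---|
| 1–2 | carry on, same dose | hold to baseline, same dose | differs on its face |
| 3 | hold to Grade 2 or less, same dose | hold to baseline, reduce | recovery level and restart dose |
| 4 | hold to Grade 2 or less, reduce or discontinue | hold to baseline, reduce | recovery level; only 5.2.5.1 offers discontinuation |

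The Grade 3 cell of Table 3 points to 5.2.5.1 for the reduction, but the pain-free Grade 3 line there contains none.

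**Step 3. Size of the Grade 3 difference**

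The dose levels are 1.8, 1.2 and 0.8 mg/kg (5.2.5 and 5.4.3). The pancreatic row gives no size for its reduction, so one level is assumed.

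- Patient on 1.8 mg/kg: 1.8 under 5.2.5.1, 1.2 under Table 3. Difference 1.8 − 1.2 = 0.6 mg/kg.
- Patient on 1.2 mg/kg in consolidation: 1.2 against 0.8. Difference 1.2 − 0.8 = 0.4 mg/kg.

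**Step 4. Doses that depend on which enzyme rose**

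Planned SGN-35 doses: 2 lead-in + 4 consolidation = 6. Scheduled draws after first exposure precede doses 2 to 6, which makes 5. Assume no rise before dose 1, three amylase episodes at the draws before doses 2, 3 and 4, and recovery within the permitted delay. The comparison is a patient with the same pattern in lipase alone whose site takes no action.

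- No episode at Grade 4: dose 2 is unchanged, dose 3 is one level lower (2nd episode), and doses 4, 5 and 6 are lost (3rd episode). Doses differing: 1 + 3 = 4 of 6.
- First episode at Grade 4: dose 2 is also reduced, or the drug is stopped at once. Doses differing: 1 + 1 + 3 = 5 of 6, or doses 2 to 6 = 5 of 6.

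If the site applies Table 3 to Grade 3 or 4 lipase rises, the lipase patient is also held and reduced, and the contrast narrows. The 3rd-episode stop still has no lipase counterpart.

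**Step 5. Reach into the primary analysis**

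Section 9.3.2 assesses complete remission at the end of AVD, before consolidation. Dose 2 is therefore the only dose after first exposure that could differ before the primary endpoint. The sample size, power and type I error do not use these rules.

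**The case against.** The strongest reply is that the cross-references run one way. The Grade 3 and 4 cells of Table 3, footnote c and Table 4 footnote 17 all send the site to 5.2.5.1. The table's wording of return to baseline and then reduction also resembles the mild-to-moderate pancreatitis bullet, so the row may have been meant for clinical pancreatitis. The remark in 5.3.3.1 that the modifications are mandatory is an aside in the AVD section and weak evidence that the table prevails. This is a coherent reading and may be the intended one. But the row is labelled only as pancreatic and is organised by grade, as the pain-free bullet is and the two symptomatic bullets are not. Nothing states precedence.

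The reply also shows that the two problems interact. If Table 3 operates in its own right, a Grade 3 or 4 lipase-only rise is held and reduced at the first occurrence. A reader might infer that repeated lipase rises lead to no automatic action at all; the documents do not support that. What is missing on either reading is the episode count and the compulsory stop.

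Stopping also remains possible. Section 10.5 lets the investigator withdraw a patient for an unacceptable adverse event, and a note in 5.2.5 allows further reductions at the PI's discretion. Both are discretionary, whereas the amylase rule is compulsory.

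Finally, a reader might connect this gap to the fatal reports in 1.6.5. Those concern acute pancreatitis, for which the symptomatic bullets already accept either enzyme. The documents do not link isolated pain-free lipase rises to harm. Whether such rises should cost a patient the study drug is a clinical choice.

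**Conclusion.** The point stands as a minor to moderate safety-instruction correction. The pain-free rule covers lipase in its heading only, so repeated lipase-only rises never reach the automatic stop. Separately, 5.2.5.1 and Table 3 give different instructions for a pain-free rise. This is clearest at Grade 3, where the next dose differs by 0.6 mg/kg, or by 0.4 mg/kg from the 1.2 mg/kg level in consolidation.

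The dose difference assumes a one-level reduction in Table 3. The counts of 4 and 5 doses assume the episode timing in Step 4 and no action on lipase under Table 3. The documents give no frequency for pain-free enzyme rises, so the number of patients affected cannot be estimated.

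Two stronger readings should be resisted. One is that Grades 1 and 2 are a demonstrated conflict. The wording differs, but the documents give no CTCAE cut-offs to show that amylase above 3 times ULN can be Grade 1 or 2. The other is that sites will in fact diverge, or that the trial's inference is at risk. Divergence is possible but not shown, and the design calculations are untouched.

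**What to change.** In 5.2.5.1, change both the entry condition and the repeat-episode rule to *amylase and/or lipase >3x ULN without abdominal pain*. State that 5.2.5.1 governs all pancreatic toxicity, and replace all four cells of the Table 3 pancreatic row with *see 5.2.5.1*. Aligning only Grades 3 and 4 would leave the Grade 1 and 2 wording in disagreement.

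The cost is a short amendment. Both enzymes are already drawn, so no new procedure is needed. There are two clinical consequences. Some patients with repeated isolated lipase rises would be reduced or stopped who are not covered by the episode rule now. The Table 3 Grade 3 reduction and the wait for baseline would no longer apply to pain-free rises. If the sponsor wants to keep those two requirements, it should move them into 5.2.5.1. If it intends the episode rule to rest on amylase alone, it should say so and remove lipase from the bullet's heading.

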- 3.3.3** Known cerebral/meningeal disease.
- 3.3.4** Any active systemic viral, bacterial, or fungal infection requiring IV treatment with antimicrobial therapy within 1 week prior to first dose.
- 3.3.5** Patients with known HBsAg positive HBV infection. Patients with prior history of Hepatitis B infection, but immune, with only IgG Hepatitis core antibody + (HBcAb +) must receive anti-viral prophylaxis (e.g., lamivudine 100mg po daily) for at least 1 week prior to cycle 1 and throughout induction and continuation therapy and for at least 6 months after the last SGN-35 dose. In addition, consultation with a hepatologist is recommended.
- 3.3.6** Patients with a known hypersensitivity to any excipient contained in the drug formulation.
- 3.3.7** Patients with dementia or an altered mental state that would preclude the understanding and rendering of informed consent.
- 3.3.8** Patients with a prior history of documented pancreatitis.
- 3.3.9** Patients with severe renal impairment (CrCL <30 mL/min). A calculated CrCl is acceptable.

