5.4.2 Dosing

Dosing of SGN-35 in this consolidation phase will start at **1.8 mg/kg or 1.2 mg/kg (depending in part on presence of neurotoxicity during SGN-35 lead-in and AVD chemotherapy)**.

5.4.2.1 The intent is to start all SGN-35 consolidation 2 weeks after the last dose/administration of AVD therapy. Furthermore, irrespective of dose, SGN-35 consolidation therapy will be given once every 3 weeks for 4 doses.

5.4.2.2 Patients who had **no neurotoxicity-related dose reductions** during the lead-in SGN-35 or vinblastine therapy may start SGN-35 consolidation at **1.8 mg/kg**.

5.4.2.3 Patients who had **any neurotoxicity-related dose reduction(s)** (or discontinuation) of the lead-in SGN-35 and/or vinblastine therapy will start SGN-35 consolidation at **1.2 mg/kg**.

5.4.2.4 If patients have **“ongoing”** grade 2, 3, or 4 neurotoxicity at the time of initiation of SGN-35 consolidation, therapy **must be delayed** until recovery to grade 1 (delay up to 8 weeks after completion of last AVD dose are permitted). If neurotoxicity does not recover to grade 1 within 8 weeks, then SGN-35 consolidation will not be given.

5.4.2.5 *Additionally*, if there are **other toxicities** whereby the treating physician believes it would be **best medical practice** to delay SGN-35 consolidation (up to 6 weeks) and/or initiate at the lower 1.2 mg/kg dose level, such decisions may be evaluated on a case-by-case basis, but should be discussed with the study PIs; the QAM should also be included on all such correspondence.

5.4.3 Dose modifications.

Intra-patient dose reduction to 1.2 mg/kg or to 0.8 mg/kg will be allowed depending on the type and severity of toxicity. Table 2 describes the recommended dose modifications for study treatment-associated toxicity. Additionally, the start of a subsequent SGN35 cycle may be delayed for up to 4 additional weeks if additional time is required for the patient to recover from study treatment-associated toxicity experienced during the current cycle.

NOTE: *SGN-35 doses reduced for treatment-related toxicity should not be re-escalated.*

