8.1.6.2 Dilution

Calculate the required volume of 5 mg/mL reconstituted brentuximab vedotin solution needed and withdraw this amount from the vials. The dose for patients with a weight of >100 kg should be calculated for 100 kg. Immediately add the reconstituted solution to an infusion bag containing a minimum volume of 100 mL to achieve a final concentration of 0.4 mg/mL to 1.8 mg/mL brentuximab vedotin. Brentuximab vedotin can be diluted into 0.9% Sodium Chloride Injection, 5% Dextrose Injection or Lactated Ringer's Injection. Gently invert the bag to mix the solution. Brentuximab vedotin contains no bacteriostatic preservatives. Following dilution, infuse the brentuximab vedotin solution immediately, or store the solution at 2-8°C (36-46°F) and use within 24 hours of reconstitution. DO NOT FREEZE.

8.1.7 **Administration. Study treatment must not be administered as an IV push or bolus.** Study treatment will be administered by outpatient IV

infusion given over approximately 30 minutes on Day 1 of each 21-day cycle. For this “lead in” phase, there are a total of 2 doses/cycles. In the absence of infusion toxicities, the infusion rate for all patients must be calculated in order to achieve a 30-minute infusion period. Study treatment will be administered through a dedicated IV line and cannot be mixed with other medications.

- **Avoid use in patients with severe renal impairment**
- **Avoid use in patients with moderate or severe hepatic impairment.**

Required Premedication and Postmedication. Routine premedication is not mandated prior to the first dose of study treatment. However, patients at clinical risk of nausea or who experience a Grade 1 or Grade 2 infusion-related reaction may receive subsequent study treatment with premedication as described below (e.g., prochlorperazine, ondansetron, etc).

8.1.8 **Incompatibilities.** No other anti-cancer treatment will be permitted during the treatment period, including chemotherapy, investigational therapies, radiation, biological response modifiers, hormone therapy, or immunotherapy.

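### The SGN-35 dose-modification rules conflict for asymptomatic pancreatic enzyme elevation and leave open whether grade 3 or higher neuropathy ends SGN-35 altogether

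*Combined protocol and SAP*

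**What the plan says.** **Pancreatic toxicity.** Table 3 has a pancreatic row. Its grade 1 and grade 2 cells read "Withhold dose until toxicity is returned to baseline, then resume treatment at the same dose level". Its grade 3 and grade 4 cells read "Withhold dose until toxicity has returned to baseline, then reduce dose, as described in section 5.2.5.1". Footnote c to the table refers the reader to Section 5.2.5.1.

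Section 5.2.5.1 distinguishes three situations. For asymptomatic enzyme elevation it grades the response, and at grades 1 and 2 the instruction is to "continue at same dose level". For mild to moderate pancreatitis it holds SGN-35 and allows resumption one dose level lower. For severe pancreatitis it stops SGN-35 permanently.

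**Status of the rules.** Section 5.2.5, the title of Table 3 and Section 5.4.3 all use the word recommended. Section 5.3.3.1, in the AVD part, says "SGN modifications are mandatory and are described above in Table 3".

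**Neuropathy.** Table 3, in the row for other non-hematologic toxicity, says "For Grade 3 or higher neuropathy, discontinue treatment". Section 5.4.2.3 covers patients with any neurotoxicity-related dose reduction ("or discontinuation) of the lead-in SGN-35 and/or vinblastine therapy will start SGN-35 consolidation at" 1.2 mg/kg). Section 5.4.2.4 delays consolidation while grade 2 to 4 neurotoxicity persists and allows it on recovery to grade 1, up to 8 weeks after the last AVD dose.

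**Hepatic warning.** Section 8.1.7 says "Avoid use in patients with moderate or severe hepatic impairment", and 8.1.12 specifies Child-Pugh B or C. The parallel renal warning has its own exclusion in 3.3.9 ("Patients with severe renal impairment (CrCL <30 mL/min"). The hepatic warning has none. The only hepatic eligibility limit is bilirubin below 3.0 mg/dl in 3.1.9.

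**The concern.** A site has to act on these rules at every SGN-35 dose. Table 4, footnote 17, requires amylase and lipase before each one, so a mandatory test feeds directly into the conflicting instructions.

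The protocol itself treats the risk as serious. Section 1.6.5 reports that acute pancreatitis contributed to a fatal outcome in 2 patient reports and that most cases arose in the first or second cycle, and the lead-in here is two cycles. The protocol history records a severe, unexpected case on this study.

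Two sites following the protocol in good faith could hold or continue SGN-35 for the same enzyme result. They could likewise end SGN-35 or restart it after the same neuropathy. A monitor would have no fixed standard for calling either a deviation. Safety of the sequence is secondary objective (b), and Section 9.5.1 tabulates adverse events by dose regimen, so those tables would partly reflect which text a site happened to follow.

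**Working it through.** No sample size, power or event count is involved, so the check sets the passages side by side.

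**Step 1: asymptomatic enzyme elevation, first episode.**

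| Grade | Table 3, pancreatic row | Section 5.2.5.1 | Difference |
|---|---|---|---|
| 1 | Withhold to baseline, then same dose | No hold, same dose | Hold or no hold |
| 2 | Withhold to baseline, then same dose | No hold, same dose | Hold or no hold |
| 3 | Withhold to baseline, then reduce | Hold to grade 2 or lower, then same dose | Recovery threshold and dose |
| 4 | Withhold to baseline, then reduce | Hold to grade 2 or lower, then reduce or discontinue | Recovery threshold; discontinuation only in 5.2.5.1 |

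The texts differ at all four grades. At grades 1 to 3 the basic action differs. At grade 4 both allow a reduced dose, so the conflict is partial.

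**Step 2: does the pointer resolve it?** The grade 3 cell says to reduce in the way 5.2.5.1 describes. For a first asymptomatic grade 3 episode, 5.2.5.1 describes no reduction; it resumes the same dose. Following the pointer therefore leads to a text that disagrees with the cell. Footnote c is a cross-reference and states no order of precedence. The grade 1 and 2 cells contain no pointer of their own; only the row's footnote mark covers them.

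**Step 3: clinical pancreatitis.** Section 5.2.5.1 classifies pancreatitis by symptoms and duration, and the protocol does not map those classes to the grades in Table 3. Without assuming a mapping, it can still be said that no pancreatic cell of Table 3 contains a permanent stop, whereas 5.2.5.1 does for severe pancreatitis.

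**Step 4: neuropathy.** The only written dose rule that discontinues lead-in SGN-35 for neuropathy is the grade 3 or higher rule in Table 3. Section 5.4.2.3 expressly includes patients whose lead-in SGN-35 was discontinued for neurotoxicity, and starts them on consolidation. Two readings follow:

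- Discontinuation ends the lead-in only. Then 5.4.2.3 and 5.4.2.4 govern what happens next and there is no conflict.
- Discontinuation ends all SGN-35. Then 5.4.2.3 restarts a drug that Table 3 has stopped.

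The table's own content shows that it is not confined to the lead-in. Several cells provide for a step from 1.2 to 0.8 mg/kg. The lead-in has two doses starting at 1.8 mg/kg, so one reduction could apply at dose 2 and a second would need a third dose. The 0.8 mg/kg step can therefore take effect only in consolidation. This does not settle which reading was meant for a patient stopped during lead-in.

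**Step 5: cross-references.** Sections 5.4.3 and 8.1.5.3 send the reader to Table 2 for SGN-35 dose modifications. Table 2 (Section 1.5) compares survival in older and younger patients. The consolidation phase thus lacks a working reference to its own dose rules.

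**The case against.** **The table defers to 5.2.5.1.** Footnote c and the grade 3 and 4 cells point there, and the history of changes suggests a residue of editing: Amendment 5 added the pancreatic modifications and Amendment 7 rewrote the graded list in 5.2.5.1. This has weight for severe pancreatitis. A reader might infer that sites cannot comply with both texts in that case, but the table refers those cells to 5.2.5.1, which is explicit about stopping. It does not cure the mismatch for asymptomatic elevation at grades 1 to 3.

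**The neuropathy texts can be harmonised.** Table 3 sits in the lead-in section, 5.2.5.1 says permanently when it means permanently, and 5.4.2.4 could be aimed at neuropathy arising on vinblastine, which 5.3.3.3 stops at grade 3. This stands as a possible reading, so the defect is an ambiguity and not a proven contradiction. A reader might also infer that every patient with grade 3 or higher lead-in neuropathy faces opposite instructions. That is not supported. Patients with documented progression after lead-in (5.2.8.1), without CR or PR after AVD (5.3.5), or without recovery to grade 1 within 8 weeks (5.4.2.4) receive no consolidation on either reading.

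**The hepatic passages do not contradict each other.** A reader might infer opposing rules here too. The warning in Section 8 already governs administration, the bilirubin limit is a partial safeguard, and no passage permits what another forbids. What remains is a minor gap between eligibility and the drug warning.

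**The results are little affected.** The primary endpoint is assessed before consolidation (9.3.2), and safety summaries describe what was actually given. Both points stand, and no bias in the CR rate is claimed.

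**Conclusion.** The pancreatic conflict is established from current text with high confidence. For asymptomatic enzyme elevation, Table 3 and 5.2.5.1 prescribe different actions at grades 1, 2 and 3, and a different recovery threshold at grade 4. No precedence is stated, and the rules are labelled both recommended and mandatory. This alone justifies correction, because it concerns a safety rule triggered by a required test.

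The neuropathy point holds as an unresolved ambiguity of scope. It affects patients who had grade 3 or higher neuropathy on lead-in SGN-35 and are otherwise eligible for consolidation. The documents give no basis for estimating how many that would be. The wrong Table 2 citations make it harder to resolve on site. The hepatic gap is minor.

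The consequence is inconsistent patient management and less interpretable safety tables. Sample size, error rates and the primary analysis are unchanged.

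**What to change.** Issue one clarifying amendment that does the following:

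- reconciles the pancreatic row of Table 3 with 5.2.5.1, so that one instruction exists for each grade and situation, and states which text takes precedence;
- reconciles the Table 3 neuropathy rule with 5.4.2.3 and 5.4.2.4, stating whether discontinuation covers the lead-in only or all SGN-35;
- says consistently, in 5.2.5, the Table 3 title, 5.3.3.1 and 5.4.3, whether the SGN-35 modifications are mandatory or recommended;
- replaces the Table 2 citations in 5.4.3 and 8.1.5.3 with the correct table;
- as a lesser item, reconciles the hepatic warning in 8.1.7 and 8.1.12 with Section 3.

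Which clinical rule to adopt in each case is for the investigators and the safety committee. The cost is the amendment and a memo to sites, with no effect on sample size, power or type I error.
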